## **Outcomes:**

### **Primary outcomes:**

The primary outcome is the mean score difference in PHQ-9 and GAD-7 scores from baseline to end of study participation, between the intervention and standard pharmacist care groups.

- Both PHQ-9 and GAD-7 are validated tools for measuring major depressive disorder and generalised anxiety, respectively, in the primary care setting. They are brief and can be self-administered, with similar results yielded with health care provider administered reports. These are desirable given the time restraints and competing demands we anticipate for community pharmacist partners participating in the study(11, 12).
- PHQ-9 scores reflect depression severity; Ranges from 0-27 (Scores: 0-4 none/minimal, 5-9 mild, 10-14 moderate, 15-19 moderately severe, 20-27 severe) (13).
- GAD-7 scores reflect anxiety severity; Ranges from 0-21 (Scores: 0-4 none/minimal, 5-9 mild, 10-14 moderate, 15-21 severe) (13)

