## **Objectives**

### **Primary objective**

To evaluate the effect (change in the mean PHQ-9 and GAD-7 score) of enhanced pharmacist care by community pharmacists with APA, in monitoring (lab ordering and interpretation, clinical monitoring of MDD and GAD), counselling (patient education), arranging referrals (in collaboration with prescribing physician), and prescribing (dose adjustment, deprescribing, and the addition of adjunctive medication) interventions for patients who have depression and anxiety and are initiated on pharmacotherapy--in comparison to the usual standard level of care conducted by pharmacist and physician.

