### **Sample size and analytical plan:**

#### Sample Size Calculation:

Lindell et al (2018), who evaluated the impact of a psychiatric clinical pharmacists intervention on the change in PHQ-9 and/or GAD questionnaire scores (14), reported a baseline PHQ-9 mean of 15.2 (Standard deviation [SD] of 6.9) and GAD mean of 12.0 (Standard deviation [SD] of 5.8).

Using those reported values and the following assumptions of an 80% power and a 2 sided alpha of 0.05, a sample size of:

- 84 patients (42 in each group) is required to detect a 4.3 point difference in the mean reduction in PHQ-9 scores between the intervention and control group
- 80 patients (40 in each group) are required to detect a 8.3 point difference in the mean reduction in GAD scores between the intervention and control group.

We selected the larger sample size of 84 patients and inflated it by 10%(47 in each group) to account for potential losses to follow-up and withdrawal of consent.

A Data Safety monitoring board will be formed to review adverse events, and data will be sent once recruitment reaches 25% (24 participant) recruitment.

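### PHQ-9 and GAD-7 are jointly primary with no rule for a positive trial: about 8-10% false positives if either scale suffices, at most 5% if both are required

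*Protocol*

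**What the plan says.** The Primary objective is worded "To evaluate the effect (change in the mean PHQ-9 and GAD-7 score) of enhanced pharmacist care". The Primary outcomes section repeats the pairing: "The primary outcome is the mean score difference in PHQ-9 and GAD-7 scores". The outcome is singular, but the instruments are two, with ranges of 0-27 and 0-21, and no composite of them is defined.

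The Sample Size Calculation treats them as two separate comparisons, under "an 80% power and a 2 sided alpha of 0.05":

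- PHQ-9: a difference of 4.3 points, 84 patients (42 per group).
- GAD-7: a difference of 8.3 points, 80 patients (40 per group).

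It then states "We selected the larger sample size of 84 patients" and inflates this by 10% to 47 per group.

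The Analytical Plan names ANCOVA for the primary outcome. It gives no order of testing, no split of alpha and no statement that both scales must succeed. The inclusion criteria admit patients with MDD, GAD or both.

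**The concern.** Two tests at the full 0.05 support different claims depending on how they are combined, and the protocol does not say how. Because the population mixes depression and anxiety, a split result (one scale significant, the other not) is quite possible. The protocol then gives no basis for calling the trial positive or negative, and the choice could be made after the results are known.

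Taking the larger of two single-scale sample sizes does not settle this. It gives each scale its own 80% power. It does not hold the error rate of an either-scale claim at 5%, and in general it does not guarantee 80% power for a both-scale claim.

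**Working it through.** **Inputs.** From the Sample Size Calculation: two-sided alpha 0.05, power 80%, PHQ-9 difference 4.3 and SD 6.9, GAD-7 difference 8.3 and SD 5.8 (both SDs are baseline values from the cited pilot), GAD-7 baseline mean 12.0, and 42 evaluable patients per group. Assumed: the correlation r between the two test statistics, which the protocol does not give and which is therefore shown from 0 to 0.8.

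**1. The plan's own sample sizes.** Per group, n = 2(1.960 + 0.842)² × SD² / difference².

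- PHQ-9: 2 × 7.849 × 6.9² / 4.3² = 40.4, so 41; the exact t-test gives 42. The stated 42 is reproduced. 42/0.9 = 46.7, so 47, also as stated.
- GAD-7 as stated: 2 × 7.849 × 5.8² / 8.3² = 7.7, so 8; the t-test gives 9. The stated 40 is not reproduced.
- GAD-7 with 3.7 (= 12.0 − 8.3): 2 × 7.849 × 5.8² / 3.7² = 38.6, so 39; the t-test gives 40. This matches the stated 40, but 3.7 appears nowhere in the protocol.

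**2. Either scale suffices: false-positive rate with no effect on either scale.** With r = 0 it is 1 − 0.95² = 0.0975. Otherwise it is 1 − P(|Z1| < 1.96 and |Z2| < 1.96) under a bivariate normal distribution with correlation r.

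| r | 0 | 0.3 | 0.5 | 0.7 | 0.8 |
|---|---|---|---|---|---|
| False-positive rate | 9.75% | 9.5% | 9.1% | 8.35% | 7.8% |

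These figures depend only on alpha and r, so the doubt about the GAD-7 difference does not touch them.

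**3. Both scales required: error rate.** If at least one scale has no effect, a false claim needs that scale to be significant, which has probability at most 0.05. The error rate is therefore at or below 5% at every r.

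**4. Both scales required: power at 42 per group.** The expected test statistic is difference/SD × √(42/2).

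- PHQ-9: 4.3/6.9 × √21 = 2.856. Power is Φ(2.856 − 1.960) = 81.5% (80.6% by t-test).
- GAD-7 at 8.3: 8.3/5.8 × √21 = 6.558. Power is about 100%.
- GAD-7 at 3.7: 3.7/5.8 × √21 = 2.923. Power is Φ(2.923 − 1.960) = 83.2%.

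Joint power from the bivariate normal distribution:

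| GAD-7 difference | r = 0 | r = 0.5 | r = 0.8 |
|---|---|---|---|
| 8.3 (stated) | 81% | 81% | 81% |
| 3.7 (assumption) | 67.8% | 72.0% | 75.8% |

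If all 47 per group were evaluable, joint power would be 85.6% with 8.3, and 74.6% (r = 0) to 80.8% (r = 0.8) with 3.7.

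**5. Either scale suffices: power.** This is the sum of the two single powers minus the joint power. Even with 3.7 it is 81.5 + 83.2 − 67.8 = 96.9% at r = 0 and 81.5 + 83.2 − 75.8 = 88.9% at r = 0.8.

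**The case against.** **The wording joins the scales with a conjunction.** Neither the objective nor the outcome says that one scale is enough, so requiring both is arguably the more literal reading, and under it there is no inflation of error. This stands as far as it goes: the 8-10% belongs to the either-scale reading only. But joining two measures in an outcome definition is not a success criterion, and nothing in the protocol excludes the looser claim.

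**The multiplicity procedure may be in the SAP.** The SAP was not available for this review, and details of testing order commonly sit there. Which measures are primary, and the alpha and power behind the sample size, are protocol matters that this protocol does fix. A later split of alpha would also not fit the chosen size: at 0.025 per scale, PHQ-9 power with 42 per group falls to about 73%, and about 49 evaluable per group would be needed for 80% (normal approximation).

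**The 0.05 and 80% are per-scale figures.** Correct. The protocol makes no explicit trial-wide claim, so the fault is a missing rule and not a false statement about overall error or joint power.

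**Putting PHQ-9 first is a preference.** This also stands. Patients with GAD only are eligible, and for them PHQ-9 is not the target measure. The order has to be the sponsor's decision.

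**Conclusion.** The point holds in limited form. Two scales share primary status, each is planned at two-sided 0.05, and the protocol has no rule for declaring success. If either scale is allowed to carry the trial, the false-positive rate is about 8-10% for correlations from 0 to 0.8; the correlation is an assumption.

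A reader might infer that the stated 5% and 80% both fail whichever way the outcome is read. The documents do not support that. Requiring both keeps the error rate at or below 5%, and on the stated inputs power is about 81%. Letting either suffice raises the error rate but leaves power above 80%.

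A reader might also take 68-76% as the trial's joint power. That range rests on replacing the stated 8.3-point GAD-7 difference with 3.7. The replacement is plausible, because it reproduces the stated 40 per group, but it is an inference. The mismatch between 8.3 points and 40 per group is a separate error, to be resolved before any joint power is quoted. All joint-power figures also assume that the stated differences and SDs apply to every patient, whether enrolled for MDD, GAD or both.

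**What to change.** Before any analysis by group, add one sentence to the protocol, carried into the SAP, that fixes one of two rules:

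1. **Fixed sequence.** Test one scale at two-sided 0.05, and the other at two-sided 0.05 only if the first is significant. PHQ-9 first is the natural example, since it sets the sample size. This holds the overall error rate at 5% whatever the correlation and keeps the planned 80% power on PHQ-9. The price is that no confirmatory GAD-7 claim is possible if PHQ-9 fails, which matters because patients with GAD only are eligible.
2. **Both required.** Keep 0.05 for each scale, say that both must be significant, and state the joint power over a range of correlations once the GAD-7 difference has been reconciled with its 40 per group. If the intended difference proves to be 3.7, the sponsor must either accept joint power of about 68-76% at 42 evaluable per group or enlarge the trial.

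Either rule costs a sentence and in itself adds no patients. Which rule, and in which order, is for the sponsor to decide.

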### **Secondary outcomes:**

- Difference in the clinical improvement rates (proportions of participants achieving clinically significant treatment response) between the pharmacist intervention and standard pharmacist care groups from baseline until the end of the study period, using the PHQ-9 and GAD-7 score.
  - For our study, clinically significant treatment response for the PHQ-9 is defined as a reduction in PHQ-9 score by at least 50% from baseline; adequate treatment response for the GAD-7 is defined as a drop in the GAD-7 score by at least 50% from baseline.
- Difference in the proportion of participants with MDD to achieve PHQ-9 score <5 (i.e. remission/no depression) between the pharmacist intervention and standard pharmacist care groups
- Difference in the proportion of participants with GAD to achieve GAD-7 score <5 (i.e. remission/no anxiety) between the pharmacist intervention and standard pharmacist care groups
- Percentage difference in self-reported safety concerns disclosed by participant to pharmacist partner anytime during the study period, between the pharmacist intervention and standard pharmacist care groups:
  - Adverse medication effects (e.g. dizziness, GI intolerance, bleeding, palpitations suggestive of prolonged QTc interval, etc.)

- Suicidal ideation, attempt at suicide
  - Causing withdrawal from study
- 

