## **Patients/Population**

### **Inclusion criteria:**

Adults  $\geq$  18 years of age, newly diagnosed with MDD and/or GAD, including:

- Patients starting on medications for the management of adults with MDD (Appendix 1) (7).
- Patients starting on medications for the management of GAD (Appendix 2) (8).

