**Exclusion criteria:**

- Pregnancy
  - Non-Alberta residents
  - Unwilling or unable to participate in regular follow-up visits
  - Unwilling to participate/sign consent form
  - $\geq 2$  suicide attempts per year
  - Severe, psychotic, and catatonic depression
  - Current substance abuse, intoxication, addiction, or withdrawal requiring acute care management
  - Patients diagnosed with comorbid anxiety disorders other than GAD, including: panic disorder, agoraphobia, specific phobia, social anxiety disorder, obsessive-compulsive disorder, posttraumatic stress disorder
  - Patients diagnosed with comorbid depressive disorder other than MDD, including: depressive disorder due to another medical condition (e.g. hypothyroidism, MS, OSA, Parkinsons, stroke, TBI, Vitamin B12 insufficiency, Huntington disease, adrenal insufficiency, mononucleosis, systemic lupus erythematosus), adjustment disorder with depressed mood
  - Patients diagnosed with concurrent ADHD, bipolar disorder, schizophrenia and schizoaffective disorder
- 

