**Recruitment:**

Potential participants will be identified and approached by the pharmacist partners (pharmacists with APA and PraCID) if they are picking up or dropping off their prescription for a medication listed in Appendix 1 and 2.

Medication indication will be verified with the patient for the treatment of diagnosed MDD and/or GAD (and if additional verification is required--collateral from physician, Netcare consult note, or pharmacy record).

As part of the standard of pharmacist practice (as outlined in the Alberta College of Pharmacist Standards of Practice for Pharmacist and Pharmacy technicians [9]), a patient is clinically assessed for pharmacotherapy appropriateness by the pharmacist partner. This process is performed by the pharmacist partner and is the initial screen to determine if the patient meets any inclusion or exclusion criteria.

Determined by the pharmacist partner, if a patient meets the inclusion criteria for the study and does not meet any exclusion criteria, the patient will be asked if he/she wants to participate in the study and be provided with a formal invite letter to review.

If the patient agrees on participating, he/she will be asked to sign a written informed consent form. After signing the consent form, the patient will be enrolled in the study and randomised as a study participant using the secured electronic study website/database (developed by EPICORE and secured at the University of Alberta research office).

The participant's physician will receive the notification letter for physicians, from the pharmacist partner, to inform him/her that the participant has agreed to participate in the study. Should the physician refuse to have the participant participate in the study, the participant will not be enrolled into the study.

Should the participant decline recruitment into the study, they will continue to receive the same level of pharmacist care as outlined in the Alberta college of pharmacists standards of practice (9).

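### Remission has no baseline condition, so participants with the diagnosis who already score below 5 at entry and stay there count as achieving remission

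*Protocol*

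**What the plan says.** The Secondary outcomes section gives two remission outcomes: "Difference in the proportion of participants with MDD to achieve PHQ-9 score <5 (i.e. remission/no depression" and "Difference in the proportion of participants with GAD to achieve GAD-7 score <5 (i.e. remission/no anxiety". Both fix a threshold and a denominator. Neither sets a condition on the baseline score or names the assessment time. The response outcome in the same section is tied to baseline: "a reduction in PHQ-9 score by at least 50% from baseline".

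Entry rests on diagnosis and treatment, not on a score. The inclusion criteria take adults "newly diagnosed with MDD and/or GAD, including" those starting a listed medication. Under Recruitment, "Medication indication will be verified with the patient for the treatment of diagnosed MDD and/or GAD". The exclusion that refers to depression severity works at the upper end: "Severe, psychotic, and catatonic depression".

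The Primary outcomes section gives the GAD-7 bands as "0-4 none/minimal, 5-9 mild, 10-14 moderate, 15-21 severe". The lowest two PHQ-9 bands have the same limits, so the remission range is the none/minimal band on both scales.

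The Both Groups section places the questionnaire at month 0 and month 6. The Randomization section has it sent after randomisation, in an electronic link that also carries the group allocation. The Analytical Plan applies intention to treat to all analyses and last observation carried forward (LOCF) to missing data.

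**The concern.** Achieving remission suggests moving from symptomatic to not symptomatic, but the definition does not require that move. A participant with MDD who scores 3 at month 0 and 3 at month 6 is counted. So is one who scores 3 at month 0 and never returns a questionnaire, because LOCF carries the 3 forward. Restricting each outcome to the matching diagnosis does not remove these cases. For example, a participant treated for both conditions may be in the lowest band on one scale and symptomatic on the other.

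The reported proportion then mixes new remission with absence of symptoms at entry. The rate rises in both arms, the difference between them shrinks, and a chance imbalance in low scorers can show up in the comparison. Adjustment for baseline score is not assured, because the plan selects covariates by a between-group p below 0.25 and allows a chi-square test.

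**Working it through.** **Inputs from the Sample Size Calculation section.** Baseline PHQ-9 mean 15.2, SD 6.9; baseline GAD mean 12.0, SD 5.8; power 80%; two-sided alpha 0.05; PHQ-9 difference 4.3 points; 42 per group, 47 after 10% inflation. The protocol gives no remission rate and no power for remission.

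**The plan's own figure.** n per group = 2 × (1.960 + 0.842)² × (6.9/4.3)² = 40.4, rounded up to 41. The t-test version gives 41.4, rounded up to 42, as stated. 42/0.90 = 46.7, rounded up to 47. The PHQ-9 sample size reproduces and this point does not affect it.

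**Share below 5 at entry, if the planning distribution applies.** Scores are whole numbers, so the cut is 4.5.

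| Model | PHQ-9 below 5 | GAD-7 below 5 |
|---|---|---|
| Normal | Φ((4.5 − 15.2)/6.9) = Φ(−1.55) = 6.0% | Φ((4.5 − 12.0)/5.8) = Φ(−1.29) = 9.8% |
| Normal truncated to the scale range | 5.2% | 8.8% |
| Beta-binomial with the same mean and SD | 7.6% | 13.1% |

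Of 94 participants this is about 5 to 7 for PHQ-9 and 8 to 12 for GAD-7. These are upper figures, because they treat all 94 as having the diagnosis concerned.

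**Dilution.** Let f be the share below 5 at entry, p the remission rate among those at 5 or more, and s the share of low scorers who finish below 5. The observed rate is (1 − f)p + fs. If s is the same in both arms, it cancels from the difference, which becomes (1 − f) times the true difference. Assume p = 25% v 45% and s = 90%; none of these is in the protocol.

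- f = 6%: 0.94 × 0.25 + 0.06 × 0.90 = 28.9%, and 0.94 × 0.45 + 0.054 = 47.7%; difference 18.8 points.
- f = 10%: 0.90 × 0.25 + 0.10 × 0.90 = 31.5%, and 0.90 × 0.45 + 0.09 = 49.5%; difference 18.0 points.
- Over the full ranges of f, the loss is 20 × f: 1.0 to 1.5 points for PHQ-9 and 1.8 to 2.6 points for GAD-7.

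**Effect on power, same assumptions, 42 per arm with the diagnosis.** With no low scorers, power for 25% v 45% is 48%. Counting low scorers as the text does gives 42% at f = 6% and 39% at f = 10%. Restricting to baseline 5 or more leaves 42 × 0.94 = 39.5 or 42 × 0.90 = 37.8 per arm and gives 46% and 44%. The restriction recovers about 4 to 5 percentage points despite the smaller denominator.

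**The case against.** The strongest reply has four parts.

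*The wording may already imply a transition, and the evaluable set can be left to a statistical analysis plan.* In part. A later plan could add a baseline condition, and the verb does suggest change. But the protocol fixes both numerator and denominator, and read literally they count these participants.

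*Being symptom-free at the end is a legitimate outcome when randomised arms are compared.* This stands. A reader might infer that the definition biases the comparison, and the documents do not support that. Randomisation spreads low scorers evenly on average, so the expected result is higher rates in both arms and a smaller difference. Mean change and 50% response are also measured elsewhere in the plan.

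*Low scorers may be rare.* This stands as a limit on the size. The planning figures come from a study of a psychiatric clinical pharmacist service, not from newly diagnosed patients starting treatment. A reader might also infer that many participants will be partly treated at baseline, since they are approached "if they are picking up or dropping off their prescription for a medication listed in Appendix 1 and 2". That does not follow: this sentence says where patients are met, while the inclusion criteria require them to be starting medication. The point does not need that argument.

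*A plain restriction to baseline 5 or more could do harm.* This stands and changes the remedy. The month 0 questionnaire is a self-report sent together with the allocation, so selecting on it could select differently in the two arms. Dropping randomised participants also departs from the intention-to-treat rule.

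**Conclusion.** The point holds as a minor flaw in the definition of two secondary outcomes. As written, a participant with the diagnosis who enters below 5 and remains there, or whose month 0 score is carried forward, counts as achieving remission.

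If the borrowed planning means and SDs apply, this concerns about 5-8% of MDD and 9-13% of GAD participants. The cost is about 1 to 2 points of an assumed 20-point difference, or 2.6 at the extreme of the GAD range. The true share could be lower or higher, and the documents cannot settle it. The remission rates and the 90% persistence are illustrative, and the dilution formula assumes equal persistence in both arms. No systematic advantage to either arm is shown, and the primary outcome and PHQ-9 sample size are untouched.

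**What to change.** In the Secondary outcomes section, define each remission outcome as a month 6 score below 5 among participants with the diagnosis whose baseline score on that scale is 5 or more, the lower limit of the protocol's mild band. Participants below 5 at baseline should be reported separately.

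In the Randomization section, have the baseline questionnaire completed before the allocation is disclosed, instead of sending both in one link.

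Alongside, report the proportion below 5 at month 6 among all randomised participants with the diagnosis, adjusted for baseline score, so that the intention-to-treat comparison is kept.

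The cost is a few lines of text, a change in the order in which the link and allocation are released, a denominator about 5-13% smaller for the restricted outcome, and one additional analysis. The participants left out could not have newly remitted.

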### **Clinical:**

- The rate of achieving remission of MDD and/or GAD compared to usual care (using PHQ-9/GAD-7)
- Cognitive and functional impairment related to MDD and/or GAD
- The occurrence of relapse of depression and/or anxiety
- The proportion of patients receiving appropriate and optimised depression and anxiety medication
- Patient complaints and/or experiences of medication-related side effects during treatment for MDD and/or GAD (i.e. GI intolerance, dizziness, weight gain)

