**Intervention Group (Pharmacist Interventions):**

Participants enrolled in the intervention group will receive pharmacist interventions, in addition to standard care outlined in the Alberta College of Pharmacist Standards of Practice for Pharmacist and Pharmacy technicians (9).

Unique pharmacist interventions will include the following (in person) at enrolment (month 0) and at the scheduled month 1, 3, and 6 in-person or telehealth pharmacist meetings:

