**Both Groups**

- Indication of medication (i.e. MDD, GAD, or both) will be recorded by the pharmacist partner in the secured study electronic website/database.
- The electronic PHQ-9/GAD-7 questionnaire (Appendix 4) will be sent securely to and completed by the participant at enrollment (month 0) and prior to the participant's in-person scheduled month 6 (final). The questionnaire results will be available to the study investigator and pharmacist participants but linked only to the participant's study ID.
- Participants will receive a pamphlet copy of Alberta Health Services Access Mental Health resource pamphlet "Know Your Addiction and Mental Health Options" which provides information regarding walk-in services, crisis support, and urgent care (10). An equivalent alternative pamphlet can be developed and provided by the study team if this document becomes obsolete or additional update/information is required.

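### The remission outcomes name no visit, while the intervention arm has three follow-up scores and the control arm one, so an any-visit count or carry-forward can favour the intervention

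*Protocol*

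**What the plan says.** Under Secondary outcomes, the Protocol lists "Difference in the proportion of participants with MDD to achieve PHQ-9 score <5" and "Difference in the proportion of participants with GAD to achieve GAD-7 score <5", each compared between arms. Neither bullet gives a visit or a period. The matching clinical secondary objective, "The rate of achieving remission of MDD and/or GAD compared to usual care (using PHQ-9/GAD-7", gives none either.

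The scoring schedule differs by arm:

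- **Intervention arm.** The first listed pharmacist task is to record PHQ-9 and GAD-7 scores. The tasks take place "at enrolment (month 0) and at the scheduled month 1, 3, and 6 in-person or telehealth pharmacist meetings".
- **Both arms.** The questionnaire is "completed by the participant at enrollment (month 0) and prior to the participant's in-person scheduled month 6 (final". The Control Group section adds no other study contact.

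The intervention arm therefore has three post-baseline scores and the control arm one.

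Three other statements bear on the point. The primary outcome runs from baseline to the end of participation. The response outcome (a fall of at least 50%) is framed from baseline to the end of the study period. The Analytical Plan fills missing data by last observation carried forward, and no data are collected from a participant after dropout.

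**The concern.** A participant can be said to achieve a score below 5 at the final visit or at any visit. With equal schedules the choice would affect both arms alike. Here it does not, because each extra visit is one more opportunity to fall below the threshold, and only the intervention arm has extra visits. An any-visit count would show a higher remission rate in that arm even if the two arms followed identical score trajectories.

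Reading the outcome at month 6 does not fully equalise the arms. Under carry-forward, an intervention participant who leaves early can contribute a month 1 or month 3 score, whereas a control participant who leaves can contribute only the baseline score.

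Remission is the first clinical secondary objective and an easily quoted result, so a difference produced by the visit schedule would matter.

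**Working it through.** **The plan's own figure.** The Protocol gives no rate or power for remission. Its one relevant number is the group size, which reproduces for the PHQ-9:

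- n = 2 × (1.96 + 0.842)² × 6.9² / 4.3² = 40.4, so 41 per group. The t-test version gives 41.4, so 42, as stated.
- 42 / 0.9 = 46.7, so 47 per group, as stated.

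**Direction under an any-visit count.** With identical arms,

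P(intervention counted) = 1 − P(month 1, month 3 and month 6 all ≥ 5) ≥ P(month 6 < 5) = P(control counted).

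The gap cannot be negative, whatever the distribution.

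**Size under an any-visit count, first set of assumptions.** The documents give only baseline PHQ-9 and GAD figures, so the follow-up inputs are assumed: normal PHQ-9 scores, SD 6, equal between-visit correlation, and remission taken as below 4.5 on the continuous scale. Both arms have the same means. There were 1,000,000 simulated participants per case. The test is z = (p_I − p_C) / √(p̄(1 − p̄) × 2/n), two-sided at 5%, with n = 47 per group.

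| Means at months 1, 3, 6 | Correlation | Month 6 only | Any visit | False gap (points) | False-positive rate |
|---|---|---|---|---|---|
| 12, 10, 9 | 0.5 | 22.7% | 35.0% | 12.3 | 26% |
| 12, 10, 9 | 0.7 | 22.7% | 31.0% | 8.3 | 15% |
| 12, 10, 9 | 0.85 | 22.6% | 27.4% | 4.8 | 8% |
| 11, 9, 8 | 0.5 | 28.0% | 42.1% | 14.1 | 30% |
| 11, 9, 8 | 0.7 | 28.0% | 37.5% | 9.5 | 17% |
| 11, 9, 8 | 0.85 | 28.0% | 33.4% | 5.4 | 9% |
| 12, 9, 7 | 0.5 | 33.8% | 44.7% | 10.8 | 19% |
| 12, 9, 7 | 0.7 | 33.9% | 40.6% | 6.8 | 10% |
| 12, 9, 7 | 0.85 | 33.9% | 37.2% | 3.3 | 6% |

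Hand check of the fourth row: p̄ = (0.421 + 0.280)/2 = 0.3505. The standard error is √(0.3505 × 0.6495 × 2/47) = 0.098, and 0.141/0.098 = 1.43. P(Z > 1.96 − 1.43) = P(Z > 0.53) ≈ 0.30.

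**Second set of assumptions.** Here remission probabilities are fixed directly, with latent correlation 0.3 to 0.9 and 42 or 47 per group.

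| Remission at months 1, 3, 6 | False gap (points) |
|---|---|
| 10, 20, 30% | 2 to 14 |
| 15, 25, 30% | 4 to 19 |
| 20, 30, 40% | 3 to 19 |
| 5, 15, 30% | 1 to 10 |

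False-positive rates run from about 5% to 47%. With month 6 used in both arms and no dropout, the gap is 0 and the rate is 4.8% to 5.8%.

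**Denominator.** The remission outcomes are restricted to participants with MDD or with GAD, and the trial enrols either or both, so fewer than 47 per arm may contribute. With 30 per arm (assumed), the 6% to 30% range becomes about 6% to 20%. The gap itself does not change.

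**Month 6 reading with carry-forward.** Let a fraction d drop out of each arm before month 6. Let q be the share of intervention dropouts whose carried month 1 or 3 score is below 5, and b the share of dropouts already below 5 at baseline. The arms then differ by d × (q − b).

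- With q = 0.20 to 0.25 and b = 0: 0.10 × 0.20 to 0.10 × 0.25 = 2.0 to 2.5 points at 10% dropout, and 4 to 5 points at 20%.
- With b = 0.06, which is Φ((4.5 − 15.2)/6.9) from the Protocol's cited baseline PHQ-9 figures: 1.4 to 1.9 points at 10% dropout, and 2.8 to 3.8 at 20%.

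The 10% matches the Protocol's allowance for losses. The values of q and the 20% are assumptions.

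**The case against.** The strongest reply is that the Protocol never says remission at any visit counts, and that its text leans towards month 6. Months 0 and 6 are the only scores the arms share, and the primary outcome is read at the end of participation. Where the outcome list wants events at any time during the study, as for safety concerns, it says so; the remission bullets do not. Carry-forward also fits an outcome read at the end. A statistical analysis plan that is not to hand could name the visit.

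Most of this stands. A reader might infer that the trial will report a false remission benefit, and the documents do not support that: the any-visit bias is conditional on a reading the text permits but does not state. A reader might also infer that the response outcome is equally undefined. It is not, since it carries a time frame, though that frame can be read as a window or as an endpoint.

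The sizes also deserve caution. The follow-up means, SD and correlations are not in the documents. Only the PHQ-9 was simulated on the score scale, and at high correlation the inflation is slight.

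The reply does not dispose of the unequal schedule, which the Protocol itself fixes, or of its combination with the stated carry-forward rule. That asymmetry remains on the month 6 reading.

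**Conclusion.** The point holds in conditional form. The remission outcomes leave the visit open, and the Protocol's arm-specific scoring makes that choice matter.

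- **Any-visit count.** The bias can only favour the intervention. Its size is about 3 to 14 points, with a false-positive rate of about 6% to 30% at 47 per group, on assumed trajectories. Broader assumptions give 1 to 19 points and about 5% to 47%. The inflation is smaller if fewer than 47 per arm have the diagnosis.
- **Month 6 reading with carry-forward.** Early scores can enter the intervention arm only. The effect is about 2 points at 10% dropout and 4 to 5 at 20%, and less if some participants are already below 5 at baseline.

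This concerns secondary outcomes. It does not touch the sample size. It should be corrected because the cost is almost nil.

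**What to change.** In Secondary outcomes, state that remission (PHQ-9 below 5, GAD-7 below 5) is assessed on the month 6 questionnaire in both arms. Say the same for response, so that its time frame cannot be read as a window.

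Add that month 1 and month 3 scores are not used in these between-arm comparisons, including through last observation carried forward. Handle a missing month 6 score by one rule for both arms, for example counted as not remitted, and make the Analytical Plan consistent with that rule. Report month 1 and 3 scores descriptively for the intervention arm.

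The cost is two or three sentences. No new data or visits are needed and nothing changes in participants' care.
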